Protocol Document

ClinicalTrials.gov Identifier: NCT05187013

Unique Protocol ID: NCR203140

Title: mHealth to Address Uncontrolled Hypertension Among Hypertensive Homeless Adults

Version Date: January 26, 2021

STUDY PROTOCOL

Project Summary

Annually, millions of Americans experience homelessness. Hypertension (HTN) is one of the most common conditions among persons experiencing homelessness (PEH) but is often uncontrolled; 40.1% of hypertensive PEH have uncontrolled blood pressure (BP) compared to 24.8% of hypertensive adults in the general population. PEH face multiple barriers to therapeutic lifestyle changes that complicate their HTN management. Strategies targeting self-management behaviors and counseling to support adherence to medications and lifestyle changes contribute to better BP control and significant cardiovascular risk reduction. However, these strategies are not available or accessible to the PEH. At the patient level, educational interventions with behavioral support through continued patient contact over months are effective in the treatment of chronic diseases including HTN. The mHealth strategies including short messaging service (SMS) texting have been shown to improve adherence to BP medications and BP control and were feasible and acceptable among hypertensive adults. Majority of the PEH have access to mobile phones that can receive and send SMS texts. Considering mobility of the PEH, we propose that an mHealth strategy using SMS texting could be used as a platform for better communication and information management for BP control, facilitate coordination of care, support behavior changes, and improve targeted outreach. The mHealth strategies for HTN have never been evaluated in the PEH despite the growing evidence of their effectiveness and the accessibility of mobile phones among PEH. This study will test this strategy and pave the way for its utilizations in the health settings where the PEH seek care and has potentials for adaptation for control of other chronic diseases among PEH. This study will be implemented in shelter-clinics in New York City (NYC) and in collaboration with community organizations making sustainability of the intervention effects and its scalability feasible. We propose a mixed methods study: AIM1: To evaluate the efficacy of a 6-month SMS texting targeted on HTN management (INT) versus an attention control (CL) on changes in systolic BP (SBP) and diastolic BP (DBP) and adherence to BP medications and appointments at 6 months in hypertensive PEH with uncontrolled BP age 21 or older (n=120). H1 Those randomized to the INT (n=60) will exhibit at least 8 mmHg reduction in either SBP or DBP compared to those randomized to the CL (n=60) at 6 months. H2 The INT group will exhibit better adherence to BP medications and appointments compared to those in the CL at 6 months. BP readings and adherence to appointments and medications will be measured at regular clinic visits. Randomization will be at the individual level in the shelter-clinics. AIM2: To assess patients' and providers' attitudes, acceptability, and experience of a 6-month mHealth SMS texting for HTN management in hypertensive PEH age 21 or older with uncontrolled BP in NYC's shelter-clinics. We will use semi-structured interviews using random and criteria sampling of the PEH and providers.

APPROACH

Overview of study design and intervention: Participants will be recruited directly in the clinics, via medical record reviews, and through the outreach team. Individual participants will be assigned to treatment groups by a computer-assisted permuted randomization schedule using of a block size of four, stratified by clinic site (n=2) a. Inclusion criteria: patient PEH age 21 or older already diagnosed with HTN whose SBP or DBP at the most recent clinic visit were >140 or >90 mmHg, respectively (see Clinic Visits) (54); English or Spanish speaking; currently presenting to the PR shelter-clinics for medical care; connected to multidisciplinary social and health services in the PR. Exclusion criteria: pregnant or within three months postpartum (55); recent heart attack or stroke (in the previous 6 months); aortic aneurysm, end stage renal disease or on dialysis; inability to read and respond to SMS texts; severe mental illness; current severe or uncontrolled substance abuse or any condition preventing participants to provide informed consent. Patients with a SBP >175 mmHg or DBP >105 are eligible only if they have no symptoms suggesting a hypertensive emergency or urgency evaluated by a medical provider (55). In these cases, providers will be given notification of intent to enroll the patient in this study and have 48 hours to opt them out of the study for any reason including mental and physical health issues. Provider participants are PR's physicians, NPs, social workers, counselors working at the sites not involved in study design or implementation. The intervention will include 6 months of mHealth HTN management support via SMS texts including reminders for medication adherence, appointment attendance, and HTN specific health education and support. The control group will receive 6

months of mHealth including basic healthcare and general health promotion via SMS texts. Both groups undergo BP measurements and adherence assessment at regular clinic visits. Participants will have a follow-up appointment scheduled at 2 months by the research associate at the baseline visit. Data obtained from patients via SMS texts is reviewed by the system and study team members. During the study, feedback to SMS texts, including automated and reciprocal feedback responding to patient-specific input, will be directly provided to the patients within the same day to enhance education and behavioral changes in a protocolized fashion. We will recruit a total of PEH (n=120) with uncontrolled HTN and a range of providers from the PR in NYC. The timeline will consist of socio-demographics and baseline data collected at the enrollment followed by a 6-month mHealth for each participant until the last enrolled participant completes the study. Primary outcomes of BP readings, medication adherence (Voils DOSE-nonadherence (68,69)), and appointment attendance will be measured at regular clinic visits. Other outcomes include phone retention rates; utilization of phones and SMS texts (# of texts read and responded by subjects). PEH with HTN and providers will be interviewed. Research assistants (RA), fluent in Spanish, will perform semi-structured interviews and collect data. Interim analysis will be performed; the final analysis of quantitative and qualitative data will ensue after the completion of data collection.

Study Procedures: Hypertensive PEH with uncontrolled BP will be identified and enrolled from the proposed site during weekdays via both electronic medical records and during their clinic visit on the day of enrollment and will be approached in the waiting rooms and offered to participate in the study. Potential unsheltered participants' eligibility will be assessed at the two predetermined clinic sites.. Uncontrolled BP is measured by the BP readings from the most recent visit (*Clinic Visit below*) and defined based on the current updated guideline and diagnoses of HTN. (54) Patient's other co-morbidities (CAD, stroke, MI, DM or chronic kidney disease) will be collected but will not be factored into eligibility assessment. The study is described to potential participants as "a study to evaluate the effect of mobile technology/SMS texts on improving HTN control for persons experiencing homelessness". If accepted, participants will be consented in a private area/room. Participants with severe mental illness or current severe or uncontrolled substance abuse will be excluded. Socio-demographics and baseline data will be collected including BP measurements by clinic nurses, and behavioral surveys, medication adherence measurements, and other data by RA. RA will offer health education on HTN for 20 minutes to all participants; provide them with free single type of cell phones (with calendar and WiFi access) with unlimited minutes and text plans for the study period; train them how to charge and maintain phones and use SMS texts; and provide ongoing help and follow-ups to assure proper understanding and usage of the phones. Lost/broken phones are replaced free of charge. At enrollment, participants will be randomly assigned to either the INT or CL group described above. Study coordinator will oversee randomization and supervise the application and implementation of the mHealth.

Brief description of mHealth/SMS texting, technology requirement, and communication venues: In initial phase of this study, to better develop and adapt the intervention, we will use a community-based participatory approach to incorporate views from a group of hypertensive PEH, shelter case workers, counselors, and providers. Using focus groups, we will explore literacy factors, HTN health literacy, and mobile technology literacy to adapt SMS platform, the intervention and its components, and evaluation tools. This process will also help further understand and address chronic diseases among other priorities. The study's AIM 1 will also help understand challenges and opportunities and refine the intervention for subsequent studies. In the INT group, participants will receive SMS texts every other day (58) to reinforce medication and appointment adherence, lifestyle changes, and health promotions related to HTN control and CVD risks. For appointment adherence, they will receive reminder SMS texts, 3 and 1 days before each appointment, with a follow up text if missed the appointment. SMS text queries will also be sent about PB medications' side effects. Texts are interactive and reciprocal; for example, if patients send texts (helping in refill medications, answering specific medication, nutrition or other questions) they will be responded within the same day by the system, or directed to an NP and or referred to the PI if need further help. For urgent matters, RA and study coordinator will direct patients to clinic providers or emergency room. If there is no response from participants after one week/three texts, the study coordinator will call to help troubleshoot or address potential reasons for dropouts. We have already identified technology companies to provide the SMS platform (English & Spanish) and IT development services for this study; evaluated their HTN management SMS platforms; and will further adapt and modify them for the intervention and attention control arms. Participants in both groups will receive welcome texts

(Thank you for participating. We will never ask for personal/banking details. Participation is voluntary etc.) and Birthday SMS-texts. Tables 1 presents brief constructs and examples of SMS texts in the INT group (29,55,59).

Table 1. Examples of intervention group's SMS texts for medication adherence in English for each construct (29,55,59)

Self-efficacy	"Have you taken all your medications in the past? Write down what helped you be successful"
Motivation	"Set a short-term goal, and achieve it! You will do whatever it takes to take your medications as prescribed"
Social Support	"Ask someone you trust to help you remember to take your medicine as directed"
Importance	"Blood pressure can't be cured. To keep healthy, keep on with your pills" "What would you say to your loved ones if they were not taking their medications? Say it to yourself"
Knowledge, attitude, barriers	"Use a pillbox to organize your medications" "Talking to your doctor or pharmacist about your medications helps you understand why you are taking them" "Leave yourself a note, voice or email to take medications"
Implementation, Intention	"Make taking your pills part of your daily routine, like brushing teeth. It helps take them regularly" "If I have 5 pills left in my bottle, I will call the pharmacy for a refill" "Going on a trip, I will pack my medicine first!"

The CL arm will receive SMS texts regarding basic general health and health promotions such as the importance of hydration (58), and safety and protection that do not overlap with HTN specific management. The INT arm also receives the same basic general health texts. Both groups will receive routine robocalls regarding their appointments and if they missed them. IT company services will be free of charge for subjects.

Clinic Visits: After enrollment, participants will be scheduled for assessment visits in the shelter-clinics to measure and record their BP readings and medication adherence at regular clinic visits. They will continue to have regular care with their respective providers at their clinics. Blood pressure is measured by clinic nurses at the initial enrollment and at each follow-ups to the end of study follow-up period for each participant.

Measurements will be taken per clinic protocols for proper blood pressure measurements (60). Since patients are already diagnosed with HTN, BP readings from the most recent visit will be used to determine uncontrolled vs controlled HTN. Uncontrolled BP is defined based on the current updated guideline (SBP>140 or DPB>90 mmHg) (54). If BP readings indicate critical values, a clinic medical provider will evaluate the patient as an urgent visit and offer the appropriate care. For medication adherence, at each assessment visits, Volis DOSe-nonadherence will be used. Since this population has unstable housing, unannounced pill counts are not feasible. Appointment attendance will be measured by accessing medical records. At enrollment, we will collect socio-demographics and clinical data including age, race/ethnicity, gender, years and episodes of homelessness, BMI, health insurance status, and history of chronic disease (diabetes, renal insufficiency, hyperlipidemia, asthma, COPD and CAD/MI, tobacco, alcohol or substance abuse, or mental illness).

Attrition/Retention: Clients at PR on average stay 1 year within the system which will decrease the attrition rate as they will be reachable in shelters; many patients continue to see their providers afterward. If no responses to texts in one week/three texts, the study coordinator will contact patients by phone and seek support from shelters case workers to connect and identify and address issues related to drop out. Multidisciplinary teams in the shelters to address social barriers and improve social services will help decrease drop-outs.

Data Management: All data received via SMS texting will be captured through the SMS texting interface developed for this project. Each enrolled participant will have a unique identifying ID that will capture their baseline and ongoing outcome data as entered by the RA. All data will be collected and sent electronically in password-encrypted files via an electronic cloud-based system to the GWU data management team that maintain and managed them. The data will be reviewed on a bimonthly basis and issues will be communicated to the contact PI to be addressed during the coordinator's periodic visits to the sites. Outlying, inconsistent data, and missing data will be the targets of the data quality review.

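### A single printed block size of four makes an expected one assignment in three certain to anyone who knows a site's earlier assignments; varying the size is a cheap, low-priority improvement

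*Protocol*

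**What the plan says.** The Overview of study design and intervention, under APPROACH, assigns individuals by a "computer-assisted permuted randomization schedule using of a block size of four, stratified by clinic site (n=2"). The 1:1 ratio is not stated as such. It follows from the arm sizes in the Project Summary, where H1 reads "Those randomized to the INT (n=60) will exhibit at least 8 mmHg reduction" and the control arm also has 60.

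Study Procedures places assignment at enrolment and gives one role two tasks: "Study coordinator will oversee randomization and supervise the application and implementation of the mHealth". The same section has the research assistant collect baseline data and then "provide ongoing help and follow-ups to assure proper understanding and usage of the phones".

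The arms differ in what they are sent. The intervention arm gets hypertension-specific messages in addition to general ones, while "The CL arm will receive SMS texts regarding basic general health and health promotions such as the importance of hydration". On access to that traffic, the Overview says "Data obtained from patients via SMS texts is reviewed by the system and study team members".

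Two statements limit what can be inferred. Patients "will be approached in the waiting rooms and offered to participate in the study", but no one is named as doing the approaching. Data Management describes the coordinator as making "periodic visits to the sites", which does not suggest someone based at a clinic.

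**The concern.** With one known block size, the end of each block can be counted off. At a given site the fourth assignment of every complete block is determined by the first three. When the first two are alike, the third is determined as well. There are only two sites, so only two sequences to follow.

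The coordinator may know the earlier assignments through overseeing randomization and the texting. The research assistant may learn individual arms while helping with phones, because the message content differs by arm. If a person who can foresee the next arm also influences who is enrolled next, or when, the arms could differ at entry in reachability or likely adherence. Both bear on the stated primary outcomes of blood pressure, medication adherence and appointment attendance.

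**Working it through.** The protocol gives no predictability figure, so there is none to reproduce.

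**Inputs.** Block size 4 and two site strata (Overview of study design and intervention); 60 per arm, hence 1:1 (Project Summary); total 120, which is 30 complete blocks. An equal split of 60 per site is an assumption. The observer is assumed to know every earlier assignment at the site, in order.

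**Certain assignments, fixed four.** There are C(4,2) = 6 equally likely orderings. In AABB and BBAA the last two places are certain; in the other four only the last is.

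- Per block: (2 × 2 + 4 × 1) / 6 = 8/6 = 1.333 of 4 places, or 33.3%.
- Over 30 blocks the count is 30 + Binomial(30, 1/3): mean 40 of 120, 95% range 35 to 45.

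**Best guess, fixed four.** The observer names the arm with more places left in the block, and ties count one half. Success by position is:

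- first: 1/2
- second: 2/3
- third: (1/3 × 1) + (2/3 × 1/2) = 2/3
- fourth: 1

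The sum is 17/6, and dividing by 4 gives 17/24 = 70.8%, or 85 of 120, against 50% by chance.

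**Varying sizes.** I simulated 40,000 site lists of 60 (20,000 two-site trials) with the sizes equally likely. The observer knows which sizes are possible and all past assignments at the site, but not the size of each block, and updates by Bayes' rule.

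| Scheme | Certain | Of 120 (95% range) | Best guess | Of 120 |
|---|---|---|---|---|
| Fixed 4 | 33.3% | 40 (35 to 45) | 70.8% | 85 |
| 4 and 6 | 5.6% | 6.7 (0 to 16) | 69.1% | 82.9 |
| 4, 6 and 8 | 2.3% | 2.8 (0 to 10) | 67.8% | 81.4 |

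A separate simulation of 3,000 site lists gave 5.6% and 69.1% for sizes 4 and 6, and 2.2% and 67.8% for sizes 4, 6 and 8.

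**Unequal sites.** For splits of 61/59, 62/58, 75/45 and 90/30, fixed four gives 38.7 to 39.0 certain. For example, 62/58 is 15 + 14 complete blocks plus two incomplete blocks of two, in which nothing is certain: 29 × 4/3 = 38.7. Sizes 4 and 6 give 6.6 to 6.7, and sizes 4, 6 and 8 about 2.8. The split hardly matters.

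**Sequence hidden.** If the observer does not know past assignments, symmetry makes each arm equally likely at every position. All three schemes then give 0 certain assignments and a 50% best guess.

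**The case against.** The strongest reply is that nothing here is an error. Blocks of four are standard, and at 60 per site they end in exact balance. The figures apply only to someone who holds a site's full ordered sequence, and the protocol does not say that the coordinator or the research assistant does. Nor does it say that either chooses whom to approach. Helping with phones might reveal single arms, but prediction needs the ordered run of earlier ones, and both arms share the same type of phone, the welcome texts, the general-health texts and the robocalls. Varying the sizes takes best-guess accuracy above chance only from 20.8 points to 19.1 or 17.8. The stronger protection is concealment of the sequence, which may be set out in a document not at hand.

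Most of this stands. It rules out any claim of demonstrated bias, and it keeps the point optional. It does not remove the point, because the block size is something the protocol itself fixes and prints, in a trial where one role oversees both randomization and texting that differs by arm. The near-disappearance of certain assignments comes from changing that printed choice alone.

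**Conclusion.** The point holds as a low-priority improvement to a valid design. Given knowledge of a site's earlier assignments, fixed blocks of four make about 40 of 120 assignments certain, against about 7 or 3 with undisclosed varying sizes. The gain against a good guesser who is not certain is small. The figures rest on 1:1 allocation, complete blocks with 60 per site, and an observer with the ordered sequence. That the last condition is met in this trial is plausible but not documented, so the figures describe exposure if it is met and do not estimate bias.

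**What to change.** Replace the fixed block of four with block sizes varying at random within site, for example 4 and 6, or 4, 6 and 8, and state in the protocol only that sizes vary. This change is worth making by itself.

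Alongside it, keep the sizes, the list and the running sequence of past assignments from whoever approaches and enrols patients. Have the list held by someone who neither enrols nor supervises the texting, since varying sizes gives no protection against a person who can see the list.

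The cost is a regenerated schedule, a named list-holder and the loss of guaranteed exact balance. At 60 per site, sizes 4 and 6 can end up to 2 participants apart per site (4 in the trial; simulated trial mean 0.8). Sizes 4, 6 and 8 can end up to 4 apart per site (8 in the trial in principle, 6 the largest simulated; mean 1.0). The sample size, visits and outcomes do not change.
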